### Other Concomitant Medications

Therapies considered necessary for the patient's well-being may be given at the discretion of the investigator and should be documented on the eCRF. Other concomitant medications, except for analgesics, chronic treatments for concomitant medical conditions, or agents required for life-threatening medical problems, should be avoided. Herbal and complementary therapies should not be encouraged because of unknown side effects and potential drug interactions, but any taken by the patient should be documented appropriately on the eCRF. Rucaparib marginally increased **digoxin** area under the plasma concentration-time curve (AUC) by 20%. Caution should be exercised for patients receiving rucaparib and requiring concomitant medication with digoxin. **Patients taking digoxin should have their digoxin levels monitored after starting rucaparib** and then regularly per standard clinical practice. In vitro, rucaparib is a potent inhibitor of MATE1 and MATE2-K, a moderate inhibitor of OCT1, and a weak inhibitor of OCT2. As inhibition of these transporters could increase metformin renal elimination and decrease liver uptake of metformin, **caution is advised when metformin is co-administered with rucaparib**. In addition, rucaparib is an inhibitor of the BCRP with 50% inhibitory concentration (IC50) value suggesting potential BCRP inhibition and increased exposures of medicinal products that are BCRP substrate (e.g., rosuvastatin).

## 7.2 Adverse Event Characteristics

- **CTCAE term (AE description) and grade:** The descriptions and grading scales found in the revised NCI CTCAE version 5.0 will be utilized for AE reporting. All appropriate treatment areas should have access to a copy of the CTCAE version 5.0. A copy of the CTCAE version 5.0 can be downloaded from the CTEP web site:  
[https://ctep.cancer.gov/protocolDevelopment/electronic\\_applications/docs/CTCAE\\_v5\\_Quick\\_Reference\\_5x7.pdf](https://ctep.cancer.gov/protocolDevelopment/electronic_applications/docs/CTCAE_v5_Quick_Reference_5x7.pdf)
- **For expedited reporting purposes only:**
  - AEs for the agent(s) that are listed above (and in the Investigational Brochures for both nivolumab and rucaparib in the appendices) should be reported only if the adverse event varies from expected toxicities (differs in nature, and/or exceeds anticipated intensity or frequency as noted in the provided expected toxicity information).
  - Other AEs for the protocol that do not require expedited reporting are outlined in Section 7.3.3 (Expedited Adverse Event Reporting under the sub-heading of Protocol-Specific Expedited Adverse Event Reporting Exclusions).
- **Attribution of the AE:**
  - Related – The AE is clearly related to the study treatment.
  - Unrelated – The AE is clearly NOT related to the study treatment.

### 7.3 Expedited Adverse Event Reporting

BMS-specific SAE reporting guidelines:

- All Serious Adverse Events (SAEs) that occur following the subject's written consent to participate in the study through 100 days of discontinuation of dosing must be reported to BMS Worldwide Safety, whether related or not related to study drug. If applicable, SAEs must be collected that relate to any later protocol-specified procedure (e.g., a follow-up skin biopsy).
- An SAE report should be completed for any event where doubt exists regarding its seriousness;
- If the investigator believes that an SAE is not related to study drug, but is potentially related to the conditions of the study (such as withdrawal of previous therapy or a complication of a study procedure), the relationship should be specified in the narrative section of the SAE Report Form.

An appropriate SAE form (e.g., USA = Medwatch form) should be used to report SAEs to BMS. If you prefer to use your own Institutional form, it must be reviewed by BMS prior to study initiation.

Note: Please include the BMS Protocol number on the SAE form or on the cover sheet with the SAE form transmission.

- The CIOMS form is available at: <http://www.cioms.ch/index.php/cioms-form-i>
- The MedWatch form is available at: [MedWatch 3500 Form](#)
- For studies with long-term follow-up periods in which safety data are being reported, include the timing of SAE collection.
- The Sponsor will reconcile the clinical database SAE cases (case level only) transmitted to BMS Global Pharmacovigilance ([[contact]](mailto:[contact])). Frequency of reconciliation should be every 3 months and prior to the database lock or final data summary. BMS GPV&E will email, upon request from the Investigator, the GPV&E reconciliation report. Requests for reconciliation should be sent to [[contact]](mailto:[contact]). The data elements listed on the GPV&E reconciliation report will be used for case identification purposes. If the Investigator determines a case was not transmitted to BMS GPV&E, the case should be sent immediately to BMS.
- BMS will notify investigators of all reported SAEs that are suspected (related to the investigational product) and unexpected (i.e., not previously described in the IB). An event meeting these criteria is termed a Suspected, Unexpected Serious Adverse Reaction (SUSAR). Investigator notification of these events will be in the form of a SUSAR Report.
  - Other important findings which may be reported by BMS as an Expedited Safety Report (ESR) include: increased frequency of a clinically significant expected SAE, an SAE considered associated with study procedures that could modify the conduct of the study, lack of efficacy that poses significant hazard to study subjects, clinically significant safety finding from a nonclinical (e.g., animal) study, important safety recommendations from a study data monitoring committee, or sponsor decision to end or temporarily halt a clinical study for safety reasons.
  - Upon receiving an ESR from BMS, the investigator must review and retain the ESR with the IB. Where required by local regulations or when there is a central IRB/IEC for the study, the sponsor will submit the ESR to the appropriate IRB/IEC. The investigator and IRB/IEC will determine if the informed consent requires revision. The investigator should also comply with the IRB/IEC procedures for reporting any other safety information.

*MCC Protocol #: MCC-18-LUN-107-CLO-PMC*

*Protocol Version and Version Date: 21.December.2022*

- In addition to the Sponsor Investigator's responsibility to report events to their local HA, suspected serious adverse reactions (whether expected or unexpected) shall be reported by BMS to the relevant competent health authorities in all concerned countries according to local regulations (either as expedited and/or in aggregate reports).

SAEs, whether related or not related to study drug, and pregnancies must be reported to BMS within 24 hours \ 1 Business Day of becoming aware of the event. SAEs must be recorded on either CIOMS, MedWatch, or approved site SAE form.

Pregnancies must be reported and submitted to BMS on any of the following form(s):

1. MedWatch or, CIOMS or
2. BMS Pregnancy Surveillance Form or,
3. Approved site SAE form

**SAE Email Address:** [[contact]](mailto:[contact])

**SAE [contact]

If only limited information is initially available, follow-up reports are required. (Note: Follow-up SAE reports should include the same investigator term(s) initially reported.)

If an ongoing SAE changes in its intensity or relationship to study drug or if new information becomes available, a follow-up SAE report should be sent within 24 hours \ 1 Business Day to BMS using the same procedure used for transmitting the initial SAE report.

**All SAEs should be followed to resolution or stabilization.**

**7.3.1 Markey Cancer Center (MCC) IITs Reporting Guidelines**

MCC IIT investigators **must** report to the PI any SAE that occurs after the initial dose of study treatment, during treatment, or within 100 days of the last dose of treatment (Nivolumab or Rucaparib) on the local institutional SAE form.

**SAEs for rucaparib must be reported to PI regardless of causality even after reporting period.**

This applies to the following categories:

- **Grade 3 (severe) Medical Events** – Events that are related or unrelated with the Intervention.
- **ALL Grade 4 (life-threatening or disabling) Medical Events** –
- **ALL Grade 5 (fatal) Events**

**Note:** If subject is in long-term follow-up, death is reported at continuing review.

7.3.2 The following table outlines the required forms and reporting structure for clinical trials.

| Study type          | Expedited reporting to MCC                   | Expedited reporting to External Agency       | Non-expedited AE  | Form  | IRB |
|----------------------------|---|---|--------------------------|--|------------|
| Industry-sponsored studies | Yes, if it meets the sponsor-required SAE reporting | Yes, if it meets the sponsor-required SAE reporting | Sponsor required process | MedWatch 3500 or 3500a per industry sponsor

OnCore for all SAEs | Yes        |

### MCC Expedited Reporting Guidelines for MCC IITs

Investigators within MCC will report SAEs directly to the MCC DSMC per the MCC DSMC SOP and UK IRB reporting policy. IRB reporting is as outlined in IRB SOP: [http://www.research.uky.edu/ori/SOPs\\_Policies/C2-0350\\_Unanticipated\\_Problems\\_Adverse\\_Events\\_SOP.pdf](http://www.research.uky.edu/ori/SOPs_Policies/C2-0350_Unanticipated_Problems_Adverse_Events_SOP.pdf)

| Attribution   | MCC Reportable SAEs |                        |                             |                        |                  |
|---|---------------------|------------------------|-----------------------------|------------------------|------------------|
|   | Grade 2 AE Expected | Grade 2 AE Unexpected  | ALL Grade 3 and Grade 4 AEs | ALL Grade 4 AE         | ALL Grade 5 AE   |
| Unrelated Unlikely  | Not required        | Not required           | Within 5 calendar days      | Within 5 calendar days | Within 24 hours* |
| Possible Probable Definite  | Not required        | Within 5 calendar days | Within 5 calendar days      | Within 5 calendar days | Within 24 hours* |
| # If listed in protocol as expected and not requiring expedited reporting, event does not need to be reported.  |                     |                        |                             |                        |                  |
| * The SAE should be reporting within 24 business hours of learning of the event for participants enrolled and actively participating in the study or for SAEs occurring within 100 days of the last intervention of Nivolumab and also Rucaparib. |                     |                        |                             |                        |                  |

### 7.3.3 Exclusions to Protocol-Specific Expedited Adverse Event Reporting

The adverse events listed below do not require expedited reporting however, they still must be reported through the routine reporting mechanism (i.e., case report form)..

| CTCAE SOC | Adverse Event                                     | Grade | Hospitalization/ Prolongation of Hospitalization | Attribution | Comments |
|-----------|---|-------|--|-------------|----------|
|           | Nausea or vomiting occurring for less than 3 days | 1 & 2 |  | All         |          |
|           | Alopecia  | All   |  | All         |          |

### 7.4 Expedited Reporting to External Agencies

Overall PI will comply with the policies of all external funding agencies and the University of Kentucky IRB regarding expedited reporting, as per the IRB’s SOP on safety reporting: [http://www.research.uky.edu/ori/SOPs\\_Policies/C4-0150-Mandated\\_Reporting\\_to\\_External\\_Agencies\\_SOP.pdf](http://www.research.uky.edu/ori/SOPs_Policies/C4-0150-Mandated_Reporting_to_External_Agencies_SOP.pdf).

Grade 5 SAEs will be also reported to BMS and Clovis Oncology within 24 hours of the learning of the event, up to the point of 100-days after the last dose of Nivolumab and Rucaparib.

#### 7.4.1 Expedited Reporting to the FDA

The Overall PI, as study sponsor, will be responsible for all communications with the FDA. The Overall PI will report to the FDA, regardless of the site of occurrence, any serious adverse event that meets the FDA's criteria for expedited reporting following the reporting requirements and timelines set by the FDA.

#### 7.4.2 Expedited Reporting to Hospital Risk Management

Participating investigators will report to the UK Office of Risk Management any participant safety reports or sentinel events that require reporting according to the institutional policy.

### 7.5 Routine Adverse Event Reporting

All AEs **must** be reported in routine study data submissions to the Overall PI on the OnCore case report forms per timeline guidance mentioned in section 7.3.3 **AEs reported through expedited processes (e.g., reported to the IRB, FDA, etc.) must also be reported in routine study data submissions.**

### 7.6 Second Malignancy

A second malignancy is one unrelated to the treatment of a prior malignancy (and is **NOT** a metastasis from the initial malignancy). Second malignancies require **ONLY** routine AE reporting unless otherwise specified.

| TP53 assay - blood collection: One 10mL Streck tube ([name] lab)  | R                | Also collected at 2-months, at 4-months; and, if applicable, at the time of disease progression.                              |                  |                                      |                                     |   |

|  |                |  |  |  |  |                 |
|--|----------------|--|--|--|--|-----------------|
| Check status of enrollment to ORIEN Protocol for Tumor Whole Exome Sequencing and Germline Mutation Testing  | R  |  |  |  |  |                 |
| Survival Status   |                |  |  |  |  | R  |

S = standard of care / R = research-related activity / QOL = quality of life

\*: A scheduling window of ± 7 days exists to accommodate adverse weather, holidays, or other issues.

\*\* These tests are not required on the Cycle 1 Day 1 visit IF evaluated during the participant’s pre-study visit.

\*\*\* : dose delays could move the visit windows out of the 7-day allowance – this will be noted in the eCRF and dates adjusted as needed.

- 1 : to ascertain eligibility of sexually active female patients who are pre-menopausal/of child-bearing potential (serum or urine pregnancy test).
- 2: CBC with diff as per Standard of Care. Only recording results for the following labs in the eCRF: ANC, Absolute lymphocytes, WBC, Platelets, and Hemoglobin.
- 3: CMP Panel includes SGOT [AST], SGPT [ALT], total bilirubin, creatinine, Albumin, alkaline phosphatase, bicarbonate, BUN, calcium, chloride, TSH, glucose, potassium, total protein, sodium.
- 4 : Cycle 1 Day 15, CMP in order to assess liver function. Only AST/ALT will be recorded in the eCRF.
- 5 : EKG at baseline, and as clinically indicated during active treatment.
- 6: Patient-Reported Outcomes assessing quality of life comprise two complementary, validated, standardized questionnaires, the EORTC QLQ-C30 and LC13. These two questionnaires will be administered at baseline (pre-treatment), at 4-months (with a +3 week window to allow this to be collected in the course of a regularly scheduled clinic visit), and at the time of disease progression (if greater than 4-months).
- 7: PBMCs for Flow Cytometry; collected for Biospecimen SRF. Each sample consists of two 8 mL BD Vacutainer CPTs with Sodium Citrate, so 16 mL is collected at pre-study, and again at Cycle 3, Day 1 (+/- 7-day study visit windows per \*).
- 8: One 10 mL whole blood draw in Streck tube up to a total of at 4 timepoints (i.e., 4 total samples collected). The timepoints for collection comprise: Pre-study; twice during active treatment (approximately every 2 months, e.g., Cycle 3 Day 1, and Cycle 5 Day1), and at time of disease progression. Samples will be processed by [name] lab.
- 9: Checking status of enrollment on ORIEN protocol, 17-MTB-01 (Yes/No status for each patient on-study).
- 10: **Survival Status** – patients are in follow-up up to 3 years post-registration. Survival will be checked every 6-months (once patient is off-treatment) up to a total of 3 years post-registration. Survival Status can be ascertained via clinic visit or phone calls.
- 11: Additionally, S/AEs will be reported per protocol, 100-days after the last dose of study drug.
- 12: **Nivolumab and Rucaparib 100-days Safety Visit reporting window:** Adverse Events for Nivolumab and Rucaparib will be monitored and reported for a 100-day period after Off-Treatment (i.e., the last dose of Nivolumab and Rucaparib per protocol). The 100-day safety visit allows a study visit window of +/- two-weeks to capture late sequelae of Nivolumab and Rucaparib, as well as any other ongoing treatment-related S/AEs).

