Effects on cardiac channel activity in vitro and a comprehensive assessment of the effects of rucaparib on electrocardiogram (ECG) parameters in cancer patients demonstrated a low risk of cardiac effects by rucaparib.

Myelodysplastic syndrome (MDS) and acute myeloid leukemia (AML) are considered adverse events of special interest (AESIs), as these events have been observed in patients exposed to cytotoxic chemotherapy (e.g., platinum and anthracyclines) used for treatment of ovarian cancer as well as with PARP inhibitors, including rucaparib. Patients in rucaparib clinical studies diagnosed with MDS or AML had significant confounding risk factors including prior cytotoxic chemotherapy, as well as deleterious BRCA mutations [28, 29]. Based on these confounding factors, there is insufficient scientific evidence to conclude that MDS and AML are causally related to rucaparib. Clovis has added these potential risks to all Informed Consent Forms (ICFs) / Patient Information Sheets (PISs). AESI's (both serious and non-serious) will be reported to Clovis within 48 hours of detection and will continue to be reported to Clovis under serious adverse event (SAE) reporting requirements.

More information on AESIs for rucaparib is provided in the rucaparib IB. This information is also found in Appendix B.

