**Table 4. Dose Modification and Re-treatment Criteria for Oral and IV Study Drugs**

| Adverse Event   | Severity (CTCAE Grade) | Oral Study Drug (rucaparib)                               |                                    | IV Study Drug (nivolumab)      |                                    |
|---|------------------------|---|------------------------------------|--------------------------------|------------------------------------|
|   |                        | Dose Modification                             | Re-treatment                       | Dose Modification  | Re-treatment                       |
| Endocrinopathy AEs    | 3                      |   |                                    | Hold                           | Grade ≤ 1 or baseline  |
| Non-hematological Toxicity (Skin)  |                        |   |                                    |                                |                                    |
| Adverse event   | 3                      | Hold  | Grade 2                | Hold                           |                                    |
| Hematological Toxicity   |                        |   |                                    |                                |                                    |
| Hematological toxicity (related events lasting >7 days for nivolumab, exceptions below) | 3-4                    | Hold    | Grade 2                | Discontinue                    |                                    |
| Confirmed MDS or AML (all new secondary malignancies are Grade 4 per CTCAE 5.0)         | 4                      | Discontinue   |                                    | Discontinue                    |                                    |
| Exceptions with nivolumab  |                        |   |                                    |                                |                                    |
| Laboratory abnormalities except as specified below                                      | 3                      |   |                                    | Hold                           | Grade ≤ 1 or baseline  |
| Thrombocytopenia > 7 days or associated with bleeding                                   | 3                      |   |                                    | Discontinue                    |                                    |

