### **Uncommon Side Effects of Rucaparib (Occurring in 0.1% to less than 1% of patients)**

Myelodysplastic syndrome (MDS) and acute myeloid leukemia (AML)a have been reported in a very small number of patients treated with rucaparib during the safety period (while on treatment with rucaparib and 28 days after last dose). MDS is a pre-cancerous condition where the bone marrow is not as good at producing blood cells (red and/or white blood cells and/or platelets). People with MDS may need transfusions (red blood cells and/or platelets) and/or other treatments. In some cases, MDS can progress to AML, which is a cancer of the bone marrow where more abnormal and immature white blood cells (also called blasts) are made than normal white blood cells. People with AML need treatment with chemotherapy and/or a bone marrow transplant. Patients may develop AML without first being diagnosed with MDS.

Events of MDS and AML have also been reported with PARP inhibitors similar to rucaparib. At this time, it is not known whether rucaparib or other PARP inhibitors cause MDS or AML, or if these developed as a result of previous chemotherapy these patients received. Your study doctor will closely monitor your blood cell levels during treatment. If he/she has any concerns about your blood counts you may be asked to have a biopsy of your bone marrow.

*a These risks have not yet been determined by Clovis as related to rucaparib. Some of these risks have been reported in a high frequency of patients in clinical trials involving rucaparib (e.g. itchy skin, rash), others have been reported in a small number of patients but pose significant risk (e.g. MDS/AML) or are generally known to be caused by other anti-cancer treatments (e.g., palmar-plantar erythrodysesthesia).*

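### After the 100-day safety visit only survival is scheduled, yet rucaparib SAE and MDS/AML reporting duties have no matching end date, so late events may be missed

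*Combined protocol and SAP*

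**What the plan says.** **Collection window.** Calendar footnote 12 says that adverse events for both drugs "will be monitored and reported for a 100-day period after Off-Treatment". Footnote 11 adds that "S/AEs will be reported per protocol, 100-days after the last dose of study drug". Section 7.3 (reports to BMS), Section 7.3.1 (SAEs to the PI), the note under the institutional expedited-reporting table, and Section 7.4 (Grade 5 events to BMS and Clovis) all use the same 100 days. The safety visit itself has a window of 14 days either side.

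**Follow-up after that.** Contacts are every 6 months, to at most 3 years from registration. As the calendar reads, adverse event evaluation, concomitant medications and blood count are empty in the Follow-Up column, and Survival Status is the one filled row. Footnote 10 states the method: "Survival Status can be ascertained via clinic visit or phone calls". Section 5.5 describes this follow-up as being for survival.

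**Duties that run longer.** Section 7.3.1 says: "SAEs for rucaparib must be reported to PI regardless of causality even after reporting period". It applies this to categories that include all Grade 4 and Grade 5 events. Section 2.3.4 makes MDS/AML an adverse event of special interest (AESI). Such events, serious or not, go to Clovis within 48 hours of being detected and "will continue to be reported to Clovis under serious adverse event (SAE) reporting requirements". Table 4 in Section 6 has the row "Confirmed MDS or AML (all new secondary malignancies are Grade 4 per CTCAE 5.0".

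**Background rate.** Appendix B places MDS/AML in the 0.1% to under 1% band and refers to cases seen "during the safety period (while on treatment with rucaparib and 28 days after last dose".

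**The concern.** A reporting duty that outlasts the last scheduled question depends on someone happening to hear of the event. Here the trial contacts survivors for up to 3 years, but the calendar does not have them asked about the one late toxicity that the protocol singles out. Section 2.3.4 names prior cytotoxic chemotherapy as a risk factor for MDS/AML, and Section 3.1.1 requires every patient to have had a platinum doublet.

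What is at stake is objective 1.2.4, the toxicity profile. If no late case is reported, a reader of the results cannot tell whether none occurred or nobody asked. Sites also face two instructions on rucaparib SAEs: a 100-day limit in several places, and a sentence that goes past it.

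**Working it through.** The plan gives no figure for this point, so there is none to reproduce. The check is a comparison of passages, followed by simple arithmetic on the length of the gap.

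**Step 1: duty against schedule**

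| Event after day 100 | Duty to report | Scheduled means of finding it |
|---|---|---|
| Death | Yes (Sections 5.5 and 7.3.1) | Survival Status every 6 months |
| New rucaparib SAE | Yes, by the open-ended sentence in 7.3.1; outside the 100-day windows elsewhere | None |
| New MDS/AML | Within 48 hours of detection (2.3.4), no end date stated | None |

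No sentence says in terms that MDS/AML must be reported after day 100. It follows by joining three passages: Section 2.3.4 sets no end date, Table 4 makes MDS/AML Grade 4, and the categories listed with the open-ended sentence in Section 7.3.1 include all Grade 4 events.

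**Step 2: length of survival-only contact**

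Inputs: 36 months of follow-up (Section 5.5); treatment up to 24 months (Section 5.4); hypothesised median PFS of 6.3 months (Section 2.2.5), used as an illustrative stopping time; 100 days = 100/30.44 = 3.3 months. Registration and first dose are taken as the same day.

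Gap = 36 − time to last dose − 3.3 months, for a patient alive at 36 months.

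- Full 24 months of treatment: 36 − 24 − 3.3 = 8.7 months.
- Treatment stops at 6.3 months: 36 − 6.3 − 3.3 = 26.4 months.

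**Step 3: allowing for deaths (illustration only)**

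The protocol states no overall survival assumption for this population. The atezolizumab trial described in Section 2.2 had medians of 10.3 and 12.3 months. Assume exponential survival from registration with median M, and treatment stopping at 6.3 months, so that collection ends at 6.3 + 3.3 = 9.6 months.

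- Alive at 36 months = 0.5^(36/M): 9% for M = 10.3 and 13% for M = 12.3.
- Mean survival-only time per enrolled patient = (M/ln 2) × [0.5^(9.6/M) − 0.5^(36/M)].
 - M = 10.3: 14.86 × (0.524 − 0.089) = 6.5 months.
 - M = 12.3: 17.75 × (0.582 − 0.132) = 8.0 months.

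The 26-month figure therefore describes a long survivor. The average enrolled patient would contribute far less.

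**Step 4: event numbers**

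The Appendix B band gives 36 × 0.001 = 0.04 to 36 × 0.01 = 0.36 expected cases. It relates to treatment plus 28 days, which lies inside the existing collection window. The documents give no rate for later onset, so the number of late cases missed cannot be calculated.

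**The case against.** The case for leaving the plan alone has several parts.

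- **Reporting does not stop.** Any case that becomes known must still be reported. The trial is single-centre, survival contacts may be clinic visits, and Section 7.3 has known SAEs followed to resolution or stabilization. This stands, and it is why late events may be missed rather than certainly will be.
- **The AESI rule may carry the SAE window.** Section 2.3.4 says continuing reports fall under SAE requirements, and the main SAE windows are 100 days. This is a fair reading. But the sentence in Section 7.3.1 expressly goes past the reporting period, so the text supports both readings.
- **The survival form may already ask.** Its content is left to a data management plan that is not among the documents. That is possible, but the calendar and footnote 10 require nothing beyond survival.
- **The scale is small.** Few patients will be alive late in follow-up, fewer than one MDS/AML case is expected even on treatment, and no efficacy estimate is affected. All of this stands and limits the weight of the point.

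A reader might make two stronger inferences that the documents do not support.

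- **That Section 7.6 diverts MDS/AML to routine reporting.** It does say "Second malignancies require" routine reporting only. But its definition is confined to malignancies unrelated to treatment of a prior malignancy, so a case attributed to earlier chemotherapy falls outside it. It also gives way where the protocol specifies otherwise, and Section 2.3.4 does. Within the window, the institutional table requires Grade 4 events within 5 calendar days whatever the attribution. What is missing is a cross-reference; the passages do not conflict.
- **That the Appendix B band measures the loss.** The chance of at least one case in 36 patients, 1 − 0.999^36 = 3.5% to 1 − 0.99^36 = 30.4%, concerns the period already covered and says nothing about late events.

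**Conclusion.** The point holds as an unreconciled reporting window with no late ascertainment scheduled. It rests on the calendar as extracted, in which Survival Status is the only Follow-Up entry, and on the plain wording of Sections 7.3.1 and 2.3.4.

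The 8.7 to 26 months of survival-only contact apply to a patient who lives to 36 months. The upper figure also treats the hypothesised median PFS as the time at which treatment stops. The consequence is that silence about MDS/AML or rucaparib SAEs after day 100 would be uninformative. The documents do not show that any given number of cases will be lost. The sample size, the primary endpoint and the planned estimates are unaffected. The change is worth making because it settles a stated safety duty at almost no cost.

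**What to change.** 1. Reconcile the open-ended rucaparib SAE sentence in Section 7.3.1 with the 100-day windows in Sections 7.3.1 and 7.4, the institutional reporting table, and calendar footnotes 11 and 12. State which events are reportable after day 100, to whom, and until when.
2. At each existing 6-monthly survival contact, add one recorded question on new MDS/AML and rucaparib SAEs. Show it in the Follow-Up column and in footnote 10.
3. As a clarification only, cross-refer Section 7.6 to the AESI rule in Section 2.3.4.

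The cost is one extra question and one eCRF field at contacts already planned, plus a few sentences of text. No visit, procedure or sample-size change is needed. With 36 patients, the question may well record few or no events, but a recorded negative answer can be interpreted and a blank cannot.
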